3.1.1 Screening Phase

Pilot Phase: Potential subjects will be identified from screening patient lists for CHOP sports medicine/physical therapy sessions. Potential subjects will be screened using the protocol inclusion and exclusion criteria. Subjects will be consented in-person at the start of their physical therapy session.

Phase 1: Potential subjects will be identified through recruitment strategies outlined in Section 8.5. Subjects will be screened over the phone, over email or in person using the protocol inclusion and exclusion criteria. Subjects will have the study explained to them and have opportunity to ask questions over the phone or in person and will sign a REDCap consent form sent to them via email. Once the consent form is signed, the study team will work with the subject to schedule a session at the Epic Sports Biomechanics research facility.

For both phases, parental/guardian permission (informed consent) and child assent, will be obtained prior to any study related procedures being performed.

3.1.2 Pilot Phase Cohort: Physical Therapy Throwing Session

During the Pilot Phase, subjects that have been identified, consented, and enrolled will wear a prototype of IDL's throwing monitor device during the duration of their physical therapy appointment. Subjects will wear the device somewhere on their arm and may or may not be asked to perform throwing movements as part of their rehabilitation regimen. This phase will test if the device is able to detect basic throwing movements and create an accurate pitch count.

3.1.3 Phase 1 Cohort: Epic Sports Biomechanics Throwing Session

During Phase 1, subjects that have been recruited, consented, and enrolled will come to the Epic Sports Biomechanics research facility on the day of their appointment. Subjects will be asked to wear the prototype device during a simulated baseball game (approximately 30-45 pitches), and then will perform a set of other baseball-specific movements while fitted with infrared markers for throwing analysis. This data will be used to develop and refine the algorithm for the prototype.

3.2 Study Duration, Enrollment and Number of Sites

3.2.1 Duration of Study Participation

The study duration per subject will be 1 day for screening, and 1 day for throwing evaluation for both the Pilot and Phase 1 groups.

3.2.2 Total Number of Study Sites/Total Number of Subjects Projected

The study will be conducted at approximately 3 investigative site in the United States: The Children's Hospital of Philadelphia, Epic Sports Biomechanics, and the University of Pennsylvania. Data will also be transferred to and analyzed at the University of Pennsylvania.

Recruitment will stop when approximately 40 total subjects are recruited. It is expected that approximately 40 subjects will be enrolled to produce 20 evaluable subjects, with 10 in the Pilot Group and 10 in the Phase 1 Group.

3.3 Study Population

3.3.1 Inclusion Criteria

Pilot Phase

- 1) Males or females age 8 to 14 years
- 2) Presenting to CHOP Physical Therapy Clinic for rehabilitation of injury that does not impede their ability to perform basic throwing movements.

Phase 1

- 1) Males or females age 8 to 14 years
- 2) Involved in official baseball team and primarily plays as the pitcher

3.3.2 Exclusion Criteria

Pilot Phase

- 1) Injury of any aspect of the throwing arm
- 2) Unwillingness to perform all requested motions

- 3) Parents/guardians or subjects who, in the opinion of the Investigator, may be non-compliant with study procedures.

Phase 1

- 1) Injury or disability impeding ability to perform normal baseball-related movements
- 2) Inability/unwillingness to schedule and/or travel to the Epic Sports Biomechanics research facility
- 3) Parents/guardians or subjects who, in the opinion of the Investigator, may be non-compliant with study schedules or procedures.

Subjects that do not meet all of the enrollment criteria may not be enrolled. Any violations of these criteria must be reported in accordance with IRB Policies and Procedures.

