8.1	CLINICAL ADVERSE EVENTS	11
8.2	ADVERSE EVENT REPORTING	11
8	STUDY ADMINISTRATION	11
9.1	TREATMENT ASSIGNMENT METHODS	11
9.2	DATA COLLECTION AND MANAGEMENT	11
9.3	CONFIDENTIALITY	12
9.4	REGULATORY AND ETHICAL CONSIDERATIONS	13
9.4.1	Data and Safety Monitoring Plan	13
9.4.2	Risk Assessment	13
9.4.3	Potential Benefits of Trial Participation	13
9.4.4	Risk-Benefit Assessment	13
9.5	RECRUITMENT STRATEGY	13
9.6	INFORMED CONSENT/ASSENT AND HIPAA AUTHORIZATION	14
9.7	PAYMENT TO SUBJECTS/FAMILIES	14
9.7.1	Reimbursement for travel, parking and meals	14
9.7.2	Payments to parent for time and inconvenience (i.e. compensation)	14
9.7.3	Payments to subject for time, effort and inconvenience (i.e. compensation)	14
9	PUBLICATION	16
10	REFERENCES	17
11	APPENDIX	17
11.1	PROPOSED DEVICE OVERVIEW	19

ABBREVIATIONS AND DEFINITIONS OF TERMS

AE	Adverse event
IDL	Innovative Design Labs
CHOP	Children's Hospital of Philadelphia
IR	Infrared

ABSTRACT

Context:

With the rise in competitive sports participation in pediatric and adolescent populations, there has also been an increase in overuse injuries. Current methods of overuse injury prevention, such as pitch-counting, fail to account for differing techniques or effort and often ignore the elevated risk for children participating in two or more sports emphasizing the same body part. This wearable device seeks to more accurately monitor overuse to prevent and aid rehabilitation of overuse injuries.

Objectives:

The primary objective of this study is to collect motion-capture data on movements common to baseball play in order to develop an algorithm for a wearable device for the prevention and rehabilitation of sports-related overuse injuries. Secondary objectives include evaluating the feasibility of wearing the throwing device during simulated baseball play.

Study Design:

Prospective reliability study.

Setting/Participants:

- Males and female baseball pitchers age 8-14 years old at the time of consent will be included
- Children with an existing injury in their throwing arm will be excluded

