4.3 Subject Completion/Withdrawal

Subjects may withdraw from the study at any time without prejudice to their care (if applicable). They may also be discontinued from the study at the discretion of the Investigator for lack of adherence to study protocols (i.e. wearing the device at appropriate times), failure to follow visit schedules, injury that prevents the subject from throwing or participating in the study, or any AEs. The Investigator may also withdraw subjects who violate the study plan, or to protect the subject for reasons of safety or for administrative reasons. It will be documented whether or not each subject completes the clinical study. If the Investigator becomes aware of any serious, related adverse events after the subject completes or withdraws from the study, they will be recorded in the source documents and on the CRF.

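### Phase 1 exclusion 1 (section 3.3.2) admits a pitcher with a current throwing-arm injury that does not impede movement, although the abstract bars that child

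*Combined protocol and SAP*

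**What the plan says.** Three places in the combined protocol and SAP deal with an injured throwing arm at entry.

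- **Abstract, Setting/Participants.** The population is described as "Males and female baseball pitchers age 8-14 years old at the time of consent will be included", followed by "Children with an existing injury in their throwing arm will be excluded". Neither line is tied to a phase.
- **Section 3.3.2, Pilot Phase, exclusion 1:** "Injury of any aspect of the throwing arm". There is no test of severity or function.
- **Section 3.3.2, Phase 1, exclusion 1:** "Injury or disability impeding ability to perform normal baseball-related movements". This covers any part of the body, but only if function is affected.

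The other two Phase 1 exclusions concern scheduling or travel and expected non-compliance. Besides age, the only Phase 1 inclusion criterion is "Involved in official baseball team and primarily plays as the pitcher" (section 3.3.1).

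Section 3.3.2 closes with "Any violations of these criteria must be reported in accordance with IRB Policies and Procedures". Section 4.3 allows discontinuation for "injury that prevents the subject from throwing or participating in the study" and adds: "The Investigator may also withdraw subjects who violate the study plan, or to protect the subject for reasons of safety or for administrative reasons".

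**The concern.** The same injury gets different answers depending on where one looks, and the looser answer belongs to the phase with the heavier stated throwing load. Pilot children make a small number of extra throws, kept inside their rehabilitation limits (section 4.2.1). Phase 1 children pitch about 30-45 times with mixed pitch types and then make overhand field throws (sections 4.2.2 and 5.1.6). No reason is given for the difference.

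Phase 1 also has no medical record review (section 5.1.1), so the team depends on what the family reports and on its own examination. Participants are aged 8 to 14 and gain no direct benefit (section 8.4.3). Whether a child with a known arm injury pitches is left to judgement on the day, although the abstract says such a child is not in the study.

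**Working it through.** No sample size, power or error rate depends on this point, so the check is a comparison of texts. The only arithmetic concerns whether the fix is affordable.

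**Test case.** A team pitcher aged 8 to 14 has a current throwing-arm injury that does not impede normal baseball movements.

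1. *Abstract:* excluded. The line has no functional qualifier.
2. *Can the abstract line be read as Pilot only?* Not comfortably. The line above it describes pitchers, and being a pitcher is a criterion only in Phase 1 (section 3.3.1).
3. *Pilot exclusion 1:* this injury would exclude a child.
4. *Phase 1 exclusion 1:* does not apply, because by construction the injury does not impede movement. Exclusions 2 and 3 are unrelated to injury.
5. *Phase 1 inclusion:* met. Under section 3.3 the child is eligible.

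**Does any later step close the gap?**

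- *Athletic history survey (4.1.2, 5.1.4):* asks about injury history after consent. No answer is stated to exclude.
- *Injury questions and physical examination (5.1.2):* done before throwing, and placed by Table 1 at the study visit rather than at screening. No finding is stated to bar throwing.
- *Monitoring by motion-analysis staff (5.3):* operates while the child performs the movements.
- *Physical therapist supervision and the child's right to stop a movement (8.4.2):* also operate during the activity.
- *Withdrawal (4.3):* the named injury ground is again functional. The safety ground could be used before the first pitch, but it is discretionary.

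Each step lowers the risk. None turns a non-impeding arm injury into a reason not to throw.

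**Room for the fix (section 6.4).** Planned Phase 1 enrolment is 20 and the evaluable target is 10, so 20 - 10 = 10 enrolled children can be lost for any reason with the target still met. A child screened out before enrolment uses none of these places. A child stopped at the pre-throw examination uses one.

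**Number affected.** The documents give no rate of current, non-impeding arm injury among youth pitchers. The count in Phase 1 could lie anywhere from 0 to 20, and nothing in the text narrows it.

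**The case against.** The strongest reply is that the abstract is only a loose summary. Its pitcher line fits Phase 1 and misdescribes the Pilot, and its arm-injury line matches the Pilot exclusion, so its two bullets may simply compress two cohorts. On that view section 3.3 governs and only the abstract needs editing. The rules may also differ for good reason. Pilot children are by definition injured, so their injury has to be kept out of the throwing arm. Phase 1 recruits active pitchers who throw as in a typical game, and a functional exclusion covering the whole body is defensible for them. Since pitching is itself a normal baseball movement, the remaining group has injuries that do not impede pitching at all.

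Much of this stands. It shows that the narrower rule could be deliberate, and it is why correcting the abstract is an acceptable alternative. It does not remove the conflict: the plan states a protection for children that the detailed criteria do not deliver, and it gives no reason.

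Three stronger readings are tempting but not supported.

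- *That enrolling such a child would escape reporting.* The reporting sentence in 3.3.2 refers to that section's criteria, but section 1.4 requires conduct in accordance with the protocol, and the abstract is part of it. How the IRB's policies would treat the case cannot be seen from the documents.
- *That injured children pitch unprotected.* Sections 4.3, 5.1.2, 5.3 and 8.4.2 say otherwise.
- *That the pitch count exceeds what these children normally throw.* The documents present it as game-like and give no usual load for comparison.

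**Conclusion.** The inconsistency is real and is in the current text. A pitcher with a current, non-impeding throwing-arm injury is excluded by the abstract and eligible under 3.3.2. For each such child the exposure is about 30-45 pitches plus an unstated number of overhand field throws in one visit. The rule applies to the 20 planned Phase 1 enrolments; how many would be affected is unknown.

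The conclusion assumes that the abstract means what it says for both phases and that impeding is read in its ordinary sense. An investigator could read that word broadly and exclude the child, but the text does not require it, and the Pilot criterion shows that an unqualified arm exclusion was available. The point should be corrected because it bears on child safety in a study without direct benefit. The existing safeguards keep it from being more serious than that.

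**What to change.** 1. In section 3.3.2, make the first Phase 1 exclusion a two-part rule: a current injury of any part of the throwing arm, or the functional criterion already there, left unchanged.
2. In section 5.1.2, add one sentence: a child with a current throwing-arm injury, reported or found before throwing starts, does not throw.
3. If the narrower Phase 1 rule is intended, correct the abstract instead so that its arm-injury line applies to the Pilot only, and give the reason.

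The first two changes cost one exclusion line and one sentence. They need no new staff, procedure or question, because the injury history and the pre-throw examination are already planned. The downside is a few more exclusions, possibly including active pitchers with minor arm complaints, since injury is not defined. A short definition would limit that loss. The allowance of 10 enrolled children in section 6.4 can absorb a few stopped at the examination.

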4 STUDY PROCEDURES

4.1 Screening Visit

4.1.1 Pilot Phase

The screening visit will occur on the day of clinic and any screening procedures (e.g. informed consent) will happen in-person. Procedures include:

- Review of inclusion/exclusion criteria
- Medical Record Review

4.1.2 Phase I cohort

For the Phase 1 cohort, the screening visit will occur over the phone or in-person. Screening procedures include:

- Informed consent (via electronic consent on REDCap distributed through email)
 - Study explanation and time for the potential subject to ask questions will occur over the phone or in person with a member of the study team
 - Subjects will be emailed an electronic consent form through REDCap, which will contain all consent-form language for their review and space for an electronic signature
- Demographics survey (on REDCap, distributed through email after consent form is received and verified)
- Complete athletic history survey (on REDCap, distributed through email after consent form is received and verified)
- Review of inclusion/exclusion criteria

4.2 Study Treatment Phase

4.2.1 Pilot Phase Study Visit

- Informed consent and assent

Subjects will be asked to put on the throwing monitor device prototype at the beginning of their physical therapy session and will wear the device for the duration of the visit or until asked by a member of the study team to remove the device. Subjects will be asked to do the following tasks while wearing the device:

- Complete any physical therapy rehabilitation exercises given by their physical therapist as part of their care
- Complete a limited number of additional throwing exercises within in the limits of the rehabilitation regimen
- Complete athletic history survey (not required to wear device for survey completion)
- Medical record review
- Height and weight measurements if not collected as part of clinical care
- Physical exam if not collected as part of clinical care
- Return throwing device at end of session or earlier if requested by study team

No subject will be asked to complete any motions or tasks that may hinder their rehabilitation regimen.

4.2.2 Phase 1 Study Visit

At the Epic Sports Biomechanics research facility, subjects will be asked to do the following activities:

- Height and weight measurements
- Physical Exam
- Wear the prototype device and participate in a simulated game
 - Pitch approximately 30-45 times using varying pitch types (fastball, change-up, etc.)
- Complete additional baseball-related movements with full the Epic Sports Biomechanics research facility monitors in a random order, including
 - Field-based overhand throws
 - Runs

- Bat swings
- Catching balls
- Return throwing device at end of session or earlier if requested by study team

4.3 Subject Completion/Withdrawal

Subjects may withdraw from the study at any time without prejudice to their care (if applicable). They may also be discontinued from the study at the discretion of the Investigator for lack of adherence to study protocols (i.e. wearing the device at appropriate times), failure to follow visit schedules, injury that prevents the subject from throwing or participating in the study, or any AEs. The Investigator may also withdraw subjects who violate the study plan, or to protect the subject for reasons of safety or for administrative reasons. It will be documented whether or not each subject completes the clinical study. If the Investigator becomes aware of any serious, related adverse events after the subject completes or withdraws from the study, they will be recorded in the source documents and on the CRF.

5 STUDY EVALUATIONS AND MEASUREMENTS

5.1 Screening and Monitoring Evaluations and Measurements

5.1.1 Medical Record Review

Patients enrolled in the Pilot Phase will undergo limited electronic medical record review of the following variables:

- Date of birth
- Height and weight
- Demographics including sex and race
- Primary diagnosis
- Prescribed physical therapy
- Medical history of current and previous injuries

Patients enrolled in Phase 1 will not necessarily be CHOP patients and thus will not undergo medical record review, but will instead be given a brief demographic survey.

5.1.2 Physical Examination

Subjects in both phases will be asked about current and past injuries. Subjects in the Pilot Phase will undergo a physical examination if not part of clinical care. The subjects in Phase 1 will also undergo a physical examination by the team prior to engaging in throwing activities. For both phases, we will be assessing height and weight as well as range of motion, strength, balance and other physical assessment measures involving the kinetic

chain that may lead to alterations in throwing technique and correspond to an increased risk of injury. Specific measurements may include range of motion of shoulder, elbow, spine, hip, and ankle; assessment for scapular dyskinesis; strength assessment through the shoulder, elbow, trunk and hip and lower extremities; single leg balance; humeral retrotorsion using musculoskeletal US will also be assessed using validated techniques.

5.1.3 LifeIMAGE/iSite

Any imaging records associated with the subjects in the Pilot Phase will be reviewed.

5.1.4 Other Evaluations, Measures

Subjects in both phases will be asked to complete a brief survey on their athletic history. The survey will ask about their athletic team involvement and injury history and should take no more than five minutes to complete. Subjects will not have to answer any questions that make them uncomfortable. This may be completed on REDCap or on paper for the Pilot Phase. Paper forms will then be entered into REDCap by a member of the study team and hard copies will be destroyed. Subjects in Phase 1 will receive the survey via email after the completed consent form has been received.

Subjects in Phase 1 will be asked to complete a brief demographic survey on REDCap, which will be sent to them via email after the study team has received their signed consent form. This survey will ask basic demographic information such as date of birth, race, and ethnicity.

5.1.5 Pilot Phase Throwing Evaluations

Subjects will wear the throwing monitor device prototype during a physical therapy session unless asked by a member of the study team to remove it. They will go through all of their normal physical therapy exercises. In addition, subjects may be asked to do a limited number of additional throwing movements during their physical therapy session. Subjects will not have to interact with the device other than donning and doffing the device. The device will collect motion data for the duration of the session. Subjects will not be asked to complete any additional exercises that could hinder their rehabilitation program. Subjects will be asked to return the throwing monitor device by the end of the study visit.

5.1.6 Phase 1 Throwing Evaluations

At the Epic Sports Biomechanics research facility, subjects will wear the throwing monitor device prototype during a simulated baseball game, pitching approximately 30-45 times using varying pitch types (fastball, change-up, etc.) as they would within a typical game. In addition, each player will perform a set of other baseball-specific movements (field-based overhand throw, run, bat swing, catch ball) typically seen in baseball play. Participants will be fitted with 51 infrared reflective markers to enable tracking of limb, torso, and head movement while actions are performed. Movement data will be video recorded and recorded with 12 Motion Analysis Raptor IR cameras encompassing a capture volume of 26ft length x 7ft width x 8ft height. A minimum of 3 time-synchronized video cameras placed at different viewing perspectives will also record participants as they perform movements. Subjects will be asked to return the throwing monitor device by the end of the study visit.

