1 BACKGROUND INFORMATION AND RATIONALE

1.1 Introduction

Overuse injuries in youth athletes are commonplace. Current methods of prevention and progressive loading during rehabilitation are rudimentary (e.g. baseball pitch count) and fail to account for the subtleties of differing player technique or effort. A system capable of quantifying biomechanical loads associated with sports movements would substantially aid physicians, therapists, guardians, and coaches in prevention and rehabilitation efforts.

Study team partners at Innovative Design Labs (IDL) in collaboration with Reality Works Inc. have developed a prototype for an advanced wearable device that has potential to track cumulative exposure to injurious forces, monitor adherence to sport-specific overuse standards and rehab regimens, and identify improper throwing technique. The purpose of this study is to collect preliminary and advanced motion data from youth athletes in order to create and refine an algorithm to quantify throwing movements, numbers, and injury associations among youth baseball players for use in this wearable throwing monitor. The Pilot Phase of the study will occur in the CHOP rehabilitation clinic while wearing the prototype device and aims to test and refine rudimentary throwing algorithms using simple throwing and movement tasks. Phase 1 of the study will occur at the Epic Sports Biomechanics research facility and will collect advanced motion-capture data during simulated baseball play in order to improve system hardware, firmware, and algorithms.

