1.2 Name and Description of Investigational Product

This sports injury performance monitoring device aims to 1) track exposure to injurious forces 2) monitor adherence to sport specific overuse standards and prescribed rehab regimens, 3) identify improper technique, and 4) meet the practical requirements of a youth-sports monitoring system (e.g. cost, aesthetics, ease-of-use, etc.). An accompanying smart phone application and web interface will be developed as part of the study for use in future product development. More information on the electronic hardware and software can be found in the Appendix, page 20.

As the comfort, ease-of-use, robustness, and appearance of any wearable device is of critical importance to its acceptance, significant effort will be put into analyzing the requirements and testing concepts for the device design in this study phase. Perfecting design and manufacturability will occur in a future study. The sensors will be sealed in soft, hypoallergenic foam to provide resistance to sweat, dirt, and physical impact. Multiple form-factors including arm-bands, elbow compression sleeves, and wrist straps will be investigated, optimizing the combination of easy donning and doffing, maximal comfort, aesthetics, and to accurate motion transfer. The system will include a “zero touch” interface where no user interaction is required to utilize the device. Study team members will be responsible for setting up, powering up, and charging the device. The case will be hermetically sealed creating a dust-tight and waterproof device (IP68 rated).

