2 STUDY OBJECTIVES

The overall purpose of the study is to create and refine an algorithm to quantify throwing movements, effort, numbers, and injury associations among youth baseball players for use in a wearable throwing monitor with the hopes of preventing and aiding in the rehabilitation of sports-related overuse injuries.

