2.1 Primary Objective (or Aim)

The primary objective of this study is to collect motion-capture data on movements common to baseball play in order to develop a wearable device for the prevention and rehabilitation of sports-related overuse injuries.

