6.3 Statistical Methods

6.3.1 Baseline Data

Data will be analyzed with the goal of determining the feasibility of the approach. The accuracy of movement classification, movement phase segmentation, mapping of sensor reading to biomechanical values, and movement detection will all be quantified. K-fold cross validation will be used to estimate the performance of regressors and classifiers. Regressor performance will be quantified via the mean and standard deviation of error values between predicted biomechanical variable values and actual values as determined from motion capture data. Biomechanical value prediction models will be considered successful if error distributions have mean and standard deviation of less than 5% and 10% respectively of the nominal value. Sensitivity and specificity will be used to quantify the

performance of movement detection and classification algorithms. Movement segment detection will be considered correct if the algorithm identifies 90% of time occupied by the movement. Detection algorithms will be considered successful if they are able to operate with specificity and sensitivity of 95%.

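### Effort is part of the study's purpose, but no procedure varies or records it, and the 5%/10% load-error rule has no benchmark to show that motion data add anything

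*Combined protocol and SAP*

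**What the plan says.** Section 2 gives the overall purpose as to "create and refine an algorithm to quantify throwing movements, effort, numbers, and injury associations among youth baseball players". Section 1.1 motivates this by saying that current prevention methods, and progressive loading in rehabilitation, "fail to account for the subtleties of differing player technique or effort". Section 2.1 aims to "develop a wearable device for the prevention and rehabilitation of sports-related overuse injuries", and section 1.2 lists among the device's aims to "monitor adherence to sport specific overuse standards and prescribed rehab regimens".

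The reference for load is motion capture (6.3.1), which is planned only in Phase 1. There, section 5.1.6 has children "pitching approximately 30-45 times using varying pitch types (fastball, change-up, etc.) as they would within a typical game", plus "a set of other baseball-specific movements (field-based overhand throw, run, bat swing, catch ball) typically seen in baseball play". Neither 4.2.2 nor 5.1.6 attaches an effort level to any of these. Under 6.3.2 the biomechanist marks phases, aborted movements and poor form, but not effort.

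The Pilot Phase recruits children in rehabilitation but excludes "Injury of any aspect of the throwing arm". It has no motion capture, and 3.1.2 limits its question to detecting throws and counting pitches.

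The success rule for load is in 6.3.1: "Biomechanical value prediction models will be considered successful if error distributions have mean and standard deviation of less than 5% and 10% respectively". Both percentages are relative to a nominal value. That section does not define the nominal value, the number of folds or the unit that is split into folds. It names no comparator.

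**The concern.** Measuring effort is what would set this device apart from a pitch count. If reference throws are never made at known, different efforts, the regression from sensor signal to joint load cannot be checked across effort, and its use on lighter rehabilitation throws is extrapolation.

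The success rule could hide this. A limit on error SD shows that a model is informative only if the quantity predicted varies by clearly more than that limit. Where a child's own pitches vary less, a prediction that ignores motion can pass. Section 5.2.1 feeds the load values into injury scores to be shown to players, parents and coaches, so an uninformative pass would be carried forward.

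**Working it through.** **Figures in the plan.** 10 evaluable Phase 1 children × 30 to 45 pitches = 300 to 450 game pitches. The limits are mean error 5% and error SD 10% of nominal. The plan gives no figure for how load varies within or between children, so the values below are assumptions: within-child CV *w* from 3% to 12%, between-child CV *b* from 0% to 30%. Nominal is taken as the observed mean load, with one load value per pitch. The simulation used 600 runs per setting.

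**1. A constant per child, folds split by pitch (10 folds assumed).** Each pitch is predicted by the mean of that child's pitches in the other folds. Mean error is about 0. Error SD ≈ *w* × √(1 + 1/*n*), where *n* is the number of that child's training pitches. With 30 pitches, *n* = 27 and the factor is 1.018. The SD is then below 10% when *w* < 10/1.018 = 9.8%. If scatter is proportional to load and *b* = 30%, a further factor √(1 + 0.30²) = 1.044 lowers the limit to 9.4%.

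| *w* | Proportion of runs passing, over *b* = 0–30% |
|---|---|
| 3–8% | 1.00 |
| 9% | 0.80–0.98 |
| 10% | 0.10–0.38 |
| 12% | 0.00 |

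**2. One pooled constant, folds split by child.** Each child is predicted by the mean of the other nine. Error SD ≈ √(*w*² + (10/9)*b*²). With *w* = 5%:

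| *b* | Error SD | Proportion passing |
|---|---|---|
| 5% | √(25 + 27.8) = 7.3% | 0.99–1.00 |
| 8% | √(25 + 71.1) = 9.8% | 0.58–0.60 |
| 10% | √(25 + 111.1) = 11.7% | 0.25–0.26 |
| 20% | √(25 + 444.4) = 21.7% | 0.00 |

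With wide differences between children, plausible at ages 8 to 14, this predictor fails.

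**3. A constant from height and weight.** If it misses a child's level with SD 7% (assumed), error SD = √(*w*² + 7²): 8.1% at *w* = 4%, 9.9% at 7%, 10.6% at 8%. Splitting by child therefore does not by itself remove the problem.

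**4. Error over the time series.** Section 6.3.2 derives load as a time series. For illustration, a half-sine load curve predicted by its mean leaves SD = √(1/2 − (2/π)²) = √(0.500 − 0.405) = 0.31 of peak. A constant fails at 31%.

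**5. Detection rule.** A detector without motion input has sensitivity + specificity = 1, against the 1.90 needed for 95% on both. It cannot pass.

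**6. Would varied effort alone repair the rule?** For three equally frequent load levels and 6% residual variation (illustrative ratios only), the error SD of a constant, as % of full load, is √(variance of levels + 6²):

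- 75/88/100: √(104.2 + 36) = 11.8%, fails.
- 85/93/100: √(37.6 + 36) = 8.6%, passes.
- 90/95/100: √(16.7 + 36) = 7.3%, passes.

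Varied effort helps only if load changes enough. A benchmark works in every case.

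**The case against.** The strongest defence is scope. Effort appears in the overall purpose and the background, but in none of the objectives in 2.1 and 2.2 or the endpoints in 6.1 and 6.2. Section 6.3.1 sets feasibility as the goal and 6.4 calls the study exploratory. A development study with 10 evaluable pitchers need not validate effort grading. That stands as a reason not to demand a redesign. It does not excuse a pass/fail rule without a comparator, or a conclusion that reaches effort and rehabilitation.

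A reader might infer that every reference pitch is thrown at full game effort by uninjured children. The documents do not say so. The typical-game wording follows the mention of pitch types and is not an effort instruction. Neither 4.2.2 nor 5.1.6 says who selects the pitch type. Phase 1 in 3.3.2 excludes only impeding injury or disability; the Abstract's exclusion of any existing throwing-arm injury is stricter, and the two need reconciling. The field-based overhand throws are a second kind of throw that adds spread in load, though without effort labels.

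A second defence is that the planned model is a regression on sensor inputs, not a constant. True, but the rule as written cannot tell the two apart when within-child spread is small.

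**Conclusion.** The point holds in limited form. Load accuracy across effort, and at reduced rehabilitation loads, cannot be shown by this study. That follows from the procedures and needs no assumed figure.

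The weakness of the 5%/10% rule is conditional. It requires one summary value per pitch, a within-child spread below about 9% of nominal, and a predictor that knows each child's level, either through folds split by pitch or through a good prediction from body size. The plan leaves the fold unit, the nominal value and the scored quantity open, so the risk is neither established nor excluded.

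A reader might go further and conclude that the trial could declare success for a device no better than a pitch count. The documents do not support that: detection must separately reach 95% on both measures, and classification and phase segmentation are also assessed.

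**What to change.** **Section 6.3.1.**
- Report the within-child slope of predicted on actual load. A constant per child gives a slope of about zero.
- Require the model's cross-validated error SD to be smaller than that of a no-motion benchmark under the same folds. The child's mean serves if folds split by pitch. If they split by child, that mean is not available from the training data, so use a prediction from height and weight, which 4.2.2 already collects.

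These are two extra summaries from data already planned.

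**Sections 4.2.2 and 5.1.6.** Log the pitch type of each pitch. This costs one column.

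**Conclusion.** Limit it to throws made without varied effort by children without an impeding injury. State that effort grading, and loads in recovering throwing arms, are not validated.

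**Reconcile the capture wording.** Sections 3.1, 3.1.3 and 4.2.2 tie infrared tracking to the additional movements, while 5.1.6 and 6.3.2 imply that pitches are captured too. If game pitches are not captured, they have no load reference.

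**Optional.** Vary instructed effort, lower than usual and in random order, among the motion-captured field-based overhand throws. Using these rather than the game pitches leaves the simulated game, and its feasibility objective in 2.2, intact. The cost is fewer field throws at usual effort. As the working shows, this supplements the benchmark and does not replace it.
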